4.3. Alternatives

There will be several tiers of risk protection implemented in the proposed clinical study.

- Risk Protection by Graft Manufacturing: The first tier of risk protection for the proposed study is in the manufacturing of BioAesthetics' NACgrafts™. Grafts will be decellularized and manufactured according to current Good Tissue Practices (CGTP) guidelines. See Investigator's Brochure and Instructions for Use.
- Risk Protection by Subject Selection Criteria: The first clinical risk mitigation strategy is to conduct a thorough subject eligibility screening according to our explicitly defined, carefully reviewed study inclusion/exclusion criteria. In addition to representing the patient characteristics defining our anticipated indications for use, these eligibility criteria ensure the selection of subjects who have an acceptably low-risk profile, and for whom participating in our study does not present a significant elevation of risk. These criteria will be identified during the recruitment process and through a review of the user's medical history. In addition, patients with characteristics that may elevate their risk of infection or injury as part of the current study will be excluded:
 - Tobacco usage
 - Delayed wound healing
 - Vitamin C deficiency
 - Diabetes
 - Uncontrolled comorbidity
 - Body mass index outside of 18.5-29.9 kg/m² range
 - Currently receiving radiation or chemotherapy, or have received radiation to breast wall

Note - these individuals will be allowed to enroll if their conditions can be resolved prior to study enrollment. We will also carefully confirm that all enrolled subjects exhibit sufficient cognitive capacities, maximizing their ability to respond appropriately in the event of any complications – e.g., by contacting study personnel.

- Risk Protection by HIPAA Compliance: Potential loss of patient privacy and confidential information is possible but is expected to be a low risk as institutional and federal HIPAA regulations will be followed to protect patient data. The clinical site will operate according to standard HIPAA-compliant procedures for handling of routine clinical data, and all research data will be entered/uploaded directly to the secure clinical study validation software on a daily basis. Hard copies of any research-specific data collection forms will be kept in a secure, locked file cabinet, to which only the clinical site's lead investigator and study coordinator will have access as designated in the final study protocol. All members of the clinical staff participating in the study will maintain strict HIPAA compliance, and the results gathered will be treated as confidential, thus requiring all staff to maintain confidentiality to minimize risk to privacy. By using standard, validated procedures and best practices for handling clinical research data wherever possible and tailoring these processes to the standard procedures and workflow of Stanford Hospital & Clinics to the extent possible, the likelihood of success will be maximized and the possibility of data breach will be minimized.
- Specific clinical study measures to manage risk will focus on routine subject monitoring in the form of weekly and monthly clinical visits. These will be conducted by a study nurse or coordinator, and include visual inspection, performed by at least one surgeon, for complications and extent of healing. During the clinical visits, patients will be prompted to answer a brief verbal survey to screen for any adverse events. Patient satisfaction will also be assessed at 6 and 12 months. If subjects exhibit symptoms indicative of adverse events requiring medical attention, which are defined by a detailed clinical decision tree, she will receive medical attention as necessary and appropriate.
- Incidental findings arising from study data will be discussed between the clinical site lead investigator and BioAesthetics' team, at regularly scheduled data review meetings.

There are no applicable alternate procedures or treatments. Any patients who exit before engraftment will not receive a NACgraft for nipple replacement. However, these patients may opt to undergo nipple reconstruction – with BioAesthetics' NACgraft™ or a commercial alternative – at a later time point. Any patients who exit after engraftment will have had nipple reconstruction and the benefits and risks associated with the NACgraft™. Current commercial alternatives include:

- Surgical techniques that create a NAC-like structure from existing local or secondary tissues or acellular dermal matrix sheets, such as Alloderm or Glyaderm
- 3D tattooing

- Cook Medical's Biodesign Nipple Reconstruction Cylinder® (BD-NRC), an acellular collagen matrix derived from porcine intestinal submucosa. BD-NRC plugs still requires the same local or secondary site nipple reconstruction.

5. INVESTIGATIONAL DEVICE INFORMATION

5.1. Investigational Device

See NACgraft™ Investigator's Brochure for complete investigational device information.

5.2. Intervention Description

This is a single-arm interventional study. The study group will undergo NAC reconstruction in the office or operating room depending on any concurrent procedures. Following antiseptics and injection of local anesthesia, an area of skin on the reconstructed breast mound is de-epithelialized with a scalpel. After obtaining hemostasis with bovie electrocautery, the graft is sewn in place using an absorbable suture. A soft dressing is then placed over the graft (antibiotic ointment, non-adherent occlusive dressing, foam/sponge dressing cut into a donut). The dressing is taken down on postoperative day 7 at the patient's first follow up appointment. Dressings are continued until epithelialization is complete over the entire graft (this is anticipated to occur over 4-6 weeks). The Foam dressings will be used for 6 weeks to prevent graft compression.

5.3. Availability

BioAesthetics Corporation will provide the NACgrafts™.

5.4. Agent Ordering

BioAesthetics will be notified upon patient enrollment and NACgrafts™ will be prepared and shipped to study site up to 3 weeks prior to engraftment.

Grafts will be sent to the Hagey Laboratory for Pediatric Regenerative Medicine at Stanford:

[name]

[name]

[contact]

The NACgrafts™ will be stored according to BioAesthetics' defined protocol prior to surgery.

5.4. Agent Accountability

The NACgrafts™ will be kept in a secure storage location, accessible only to study personnel, to avoid access to unauthorized persons.

6. DOSE MODIFICATIONS

Due to the nature of the device, dose modifications are not relevant to this study.

7. ADVERSE EVENTS AND REPORTING PROCEDURES

7.1. Potential Adverse Events

The potential risks have been identified below. The existing standard of care would be applied to any adverse event. More detailed risk mitigation strategies are described in section 4.3 – Alternatives.

Loss of Privacy and Confidentiality: Potential loss of patient privacy and confidential information is possible.

Medical Risks: The potential risks will be summarized in the consent form and will be reviewed with the patient by the surgeon or study coordinator (as designated in the final protocol). Patients will additionally be able to access a member of the study team with any questions pertaining to risks for this study.

Since a surgical procedure is required for the placement of the BioAesthetics NACgraft™, there are several expected adverse events that are related to the surgery itself. These are similar to the risks with any nipple reconstruction procedure and they include:

- Swelling/edema
- Infection
- Wound contracture
- Pain
- Bleeding
- Lack of or abnormal sensation
- Unanticipated cosmetic result
- Asymmetry
- Scarring
- Need for revisionary procedures

Adverse events that may result from the use of NACgraft™ itself include, but are not limited to the following:

- Lack of device integration
- Lack of device epithelialization
- Device slough
- Abnormal coloration with healing
- Allergic reaction to remaining trace amounts of processing reagents listed in the Cautions section.
- Graft rejection
- Transmission of known pathogens including Hepatitis B or C, HIV I/II, syphilis or other bacteria.
- Transmission or causation of diseases of unknown etiology and characteristics.

7.2. Adverse Event Reporting

Adverse events will be graded according to CTCAE v4.03. Both Serious and Non-Serious Adverse Events will be clearly noted in source documentation and listed on study specific Case Report Forms (CRFs). The Protocol Director (PD) or designee will assess each Adverse Event (AE) to determine whether it is unexpected according to the Informed Consent, Protocol Document, or Investigator's Brochure, and related to the investigation. All Serious Adverse Events (SAEs) will be tracked until resolution, or until 30 days after the study

treatment.

SAEs CTCAE Grade 3 and above, and all subsequent follow-up reports will be reported to the Stanford Cancer Institute Data and Safety Monitoring Committee (DSMC) using the study specific CRF regardless of the event's relatedness to the investigation. Following review by the DSMC, events meeting the IRB definition of 'Unanticipated Problem' will be reported to the IRB using eProtocol within 10 working days of DSMC review, or within 5 working days for deaths or life-threatening experiences.

8. CORRELATIVE/SPECIAL STUDIES

No further correlative laboratory or animal studies are planned.

9. STUDY CALENDAR

	Screening	Day 0	Day 7 ^a	Day 14 ^a	Day 28 ^a	Day 42 ^a	Day 90 ^a	Day 180 ^a	Day 360 ^a	Personnel	Description
Informed Consent	X									Study Site Staff	
Height and Weight (for BMI)	X									Study Site Staff	
Medical History	X									Study Site Staff	
Vital Signs	X	X	X	X	X	X	X	X	Study Site Staff		Patient vital signs (heart rate, blood pressure, temperature) will be taken with the patient in a seated position and medications will be recorded.
Current Medications	X	X	X	X	X	X	X	X	Study Site Staff		
NACgraft Engraftment		X								Surgeon	
Surgical Time		X							Study Site Staff		Duration will be the time difference between initial incision of the wound bed (i.e. de-epithelialization) and placement of the final suture.
Discontinue Nipple Protector					X				Surgeon		The use of nipple protector bandage will be discontinued after 6 weeks ^b .
Photographs ^a	X	X	X	X	X	X	X	X	Study Site Staff		Digital photographs of each NACgraft will be taken for documentation and transmission to surgeon for specified endpoints.
Wound Healing			X	X	X	X	X	X	Surgeon		Visual inspection of the graft(s) will be conducted to assess the extent of NACgraft healing and identify any complications (e.g. necrosis, infection). Assessments will be performed by the study site Surgeon and, using the photographs. Wound healing will be assessed via the following metrics: epithelialization (0-100%), granulation (0-100%), ischemia/necrosis (0-100%), dehiscence (0-100%), and overall healing (0-100%).
Infection			X	X	X	X	X	X	Surgeon		Grafts will be assessed for infection via the following metrics: A) no infection; B) hyperemia (no infection); C) cellulitis (superficial infection); D) abscess or purulent infection.
Vascularity					X	X	X	X	X	Surgeon +	An assessment of blood flow to the NAC will be determined visually both by the surgeon and, using the digital photographs, by surgeon.. The NAC color will be graded as white, pink, light brown, blue, purple or black. In addition, each NACgraft will be pricked with a lancet/lancing device (the type used for obtaining fingerstick glucose measurement) in each quadrant of the areola, plus the nipple, for a total of 5 regions to determine vascularization. Lancing will be discontinued after the first post-operative visit demonstrating vascularity.
Graft Dimensions					X	X	X	X	Study Site Staff		Nipple projection/height and diameter will be measured with a Depth Gauge and Drill Gauge, respectively.
NAC Sensitivity	X					X	X	X	Surgeon		Sensitivity testing will be performed with the patient laying down and eyes closed. The areola will be divided into 4 quadrants, plus the nipple, for a total of 5 regions to be tested using the Semmes Weinstein monofilament technique.
Patient Surveys	X					X	X	X	Study Site Staff		Patients will complete the Nipple Reconstruction Satisfaction Survey – Pre at Screening and Nipple Reconstruction Satisfaction Survey – Post at Days 90, 180, and 360.

a: window +/- 4 days| b: subject discretion and/or PI discretion to continue beyond 6 weeks

10. MEASUREMENTS

10.1. Primary outcome measure: time to complete healing

10.1.1. Relevant Subset

All patients (n=15).

10.1.2. Measurement Definition

Time to healing for each NACgraft will be as the first weekly visit at which the surgeon deems the graft >99% overall healed. This measurement will be reported as the number of weeks to healing.

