4. TREATMENT PLAN

On the day of surgery, NACgrafts™ will be engrafted according to standard reconstructive technique. Using sterile technique, the recipient site on the breast mound will be de-epithelialized sharply and meticulous hemostasis obtained with electrocautery. The NACgraft™ will then be sutured into the wound bed with dissolving suture (e.g., chromic gut). In women undergoing bilateral NAC reconstruction, this process will be repeated for the contralateral breast. A sterile dressing will be applied, and patients will be discharged home according to institutional guidelines; written instructions will be provided for the care of the NACgraft(s)™ and dressings. The dressing will include antimicrobial ointment, followed by a non-adherent, occlusive dressing (e.g. Adaptic, Xeroform) secured in place using a foam dressing cut into a donut (e.g., Allevyn) to prevent compression of the graft.

Patients will be return to the outpatient clinic regularly until the graft(s) are fully healed: on or about postoperative Days 7, 14, 28, and 42. They will return on days 90, 180, and 360 for measurement of long-term endpoints including nipple dimensions, sensitivity, and for satisfaction survey completion.

In the event that the NAC Graft fails, the surgeon will determine if re-grafting is appropriate. The patient will be offered to undergo a second NAC Graft procedure.

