10.1.3. Measurement Methods

Degree of healing will be based on visual assessment by the surgeon with the following metrics on a visual analog scale (VAS): vascularization, overall healing (0-100%). Photographs will be taken, stored and transmitted securely to BOX. Time to complete healing will be defined as the first visit at which the surgeon determine that there is >99% overall healing of the graft.

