10.1.4. Measurement Time Points

Healing assessment will take place at each postoperative visit until healed including day 7, 14, 28, and 42. Further early postop follow up visits may be considered as determined by the surgeon.

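### The primary healing time has two definitions, a weekly label that the visit calendar does not support, and no rule for a graft that never heals

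*Combined protocol and SAP*

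**What the plan says.** - **Definition.** Section 10.1.2: "Time to healing for each NACgraft will be as the first weekly visit at which the surgeon deems the graft >99% overall healed". Section 12.4.2 agrees. Section 10.1.3 drops the word weekly and has "the first visit at which the surgeon determine that there is >99% overall healing of the graft". The synopsis keeps weekly but asks for more than 99% epithelialization. The Wound Healing row of the Section 9 calendar lists epithelialization and overall healing as separate 0-100% scores.
- **Visits.** Section 10.1.4: "Healing assessment will take place at each postoperative visit until healed including day 7, 14, 28, and 42", followed by "Further early postop follow up visits may be considered as determined by the surgeon". Section 4 has patients return "regularly until the graft(s) are fully healed: on or about postoperative Days 7, 14, 28, and 42". Section 2.4 puts later visits at Days 90, 180 and 360, and the calendar footnote allows 4 days either side. Section 4.3 nevertheless describes "routine subject monitoring in the form of weekly and monthly clinical visits".
- **Expected timing.** Section 5.2 continues dressings until "epithelialization is complete over the entire graft (this is anticipated to occur over 4-6 weeks").
- **Failures.** Section 7.1 lists failure to epithelialize among device risks. Section 4.2 foresees removal of the graft and withdrawal. Section 4 says of a failed graft: "The patient will be offered to undergo a second NAC Graft procedure".
- **Analysis.** Section 12.4.1 includes all participants on an intention-to-treat basis. Section 12.4.2 reports the maximum, mean, median and a 95% confidence interval, and Section 12.3 names the t distribution.
- **Use.** Section 12.6.2 wants the estimates and their variability for sizing a larger study. Section 12.7 makes a healing rate above 95% one of its conditions for going on, with no serious adverse events and adequate survey scores.

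**The concern.** Healing time is one of two primary outcomes, and two analysts following the text could report different results from the same data. They could choose different scales. They could also differ on nominal weeks or actual days, on what to do with a graft that never heals, and on whether the unit for Section 12.7 is the patient or the graft. The widest early gaps between visits lie where the protocol itself expects healing to finish. A summary restricted to healed grafts says nothing about failures, yet failure is among the things that a first pilot of this device needs to show.

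**Working it through.** The plan gives no derived figure to reproduce: 15 patients is a pilot size, and Section 12.6.3 declares effect size not applicable. No healing distribution is given either, so the simulated figures below are illustrations.

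**1. Definitions side by side**

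| Place | Visit | Scale |
|---|---|---|
| Synopsis | first weekly | epithelialization >99% |
| 10.1.2 and 12.4.2 | first weekly | overall healing >99% |
| 10.1.3 | first | overall healing >99% |

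Because the calendar scores the two scales separately, one graft can receive two different times.

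**2. Gaps between scheduled visits (weeks).** 7/7 = 1; (14-7)/7 = 1; (28-14)/7 = 2; (42-28)/7 = 2; (90-42)/7 = 6.9. Nothing is scheduled at weeks 3 or 5.

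**3. What is recorded.** For true healing day T, the record is the first visit day on or after T.
- At nominal days, T from 29 to 42 gives 42/7 = 6.0 weeks. T = 43 gives 90/7 = 12.9 weeks unless an extra visit takes place.
- The table shows recorded mean/SD in weeks for assumed healing times. Windows are drawn evenly from -4 to +4 days, and the extra visits are assumed at weeks 8 and 10.

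| Assumed healing | True | Windows, no extra visits | Windows, extra visits |
|---|---|---|---|
| Even over 4-6 weeks | 5.0/0.58 | 6.45/1.96 | 6.07/0.79 |
| Normal, mean 5, SD 1 | 5.0/1.0 | 6.91/2.85 | 6.07/1.20 |

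At nominal days the first row reads 6.0 with SD 0. With windows and no extra visits, 8% of its grafts are read near Day 90. For the second row, exactly weekly visits would give 5.50/1.04, and extra visits at weeks 3, 5, 7, 8 and 10 about 5.6/1.10.

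**4. Grafts that never heal.** Take a hypothetical 15 grafts, 5 recorded at week 4 and 10 at week 6. Let some of the week-6 grafts fail and drop out of the mean:
- 0 failures: (5×4 + 10×6)/15 = 5.33
- 1 failure: (5×4 + 9×6)/14 = 5.29
- 2 failures: (5×4 + 8×6)/13 = 5.23
- 3 failures: (5×4 + 7×6)/12 = 5.17

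In this example the healed-only mean improves as failures rise. With 2 failures the mean is 5.33 if they are set to week 6, 6.25 if set to Day 90 and 11.39 if set to Day 360. The plan selects none of these.

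**5. Two grafts in one patient.** Coverage of a graft-level 95% t interval for the mean first-visit time was simulated with healing normal (mean 5, SD 1 week) and 20,000 trials. With all 15 patients bilateral and within-patient correlation 0.5 to 0.8, it is about 85 to 89% without extra visits and 87 to 90% (91% in another run) with them. With 5 bilateral patients, correlation 0.5 and extra visits, it is about 93%.

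**6. The Section 12.7 healing rate.** With one unhealed graft, per patient: 14/15 = 93.3%, missed. Per graft, with b bilateral patients, g = 15 + b and the rate is (g-1)/g. At g = 20, 19/20 = 95.0%, which does not exceed 95%. At g = 21, 20/21 = 95.2%, which does. So the per-graft criterion is met when 6 or more patients are bilateral.

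**The case against.** This is a 15-patient descriptive pilot that disclaims definitive conclusions. Three of the four definitions agree on overall healing; only the synopsis differs. Patients return until healed, and the surgeon may add visits, which could fill the gaps at weeks 3 and 5 and make a jump from Day 42 to Day 90 unlikely. Failures remain visible in percent healed over time (synopsis) and in the complication data (Section 10.2).

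Much of this stands, and it rules out three stronger readings that a reader might infer.

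- **That the recorded SD would missize the next study.** The measure is first-visit time, so its SD is the right one for a study on the same visits. Sample sizes worked out from recorded differences and SDs gave simulated power of 79% and 82% against a target of 80%.
- **That the healing criterion would be missed at Day 42.** Nothing ties Section 12.7 to Day 42; its wording reads most naturally as study completion. If healing is even over 4-6 weeks, every graft is healed at a nominal Day 42 visit. A shortfall appears only if visits are assumed to spread across Days 38 to 46.
- **That the t interval is badly wrong in general.** It targets the mean first-visit time as defined. The lowest coverage needs all patients bilateral. Even with no bilateral patients and no extra visits it is about 92 to 93%, so part of the shortfall is skew from Day 90 readings.

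What the objection does not remove: none of the extra visits is fixed, the synopsis still conflicts with the body, no passage handles an unhealed graft, and Section 12.7 names neither unit nor denominator.

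**Conclusion.** The point holds as a defect of definition and analysis that should be fixed. Four things are certain from the text alone: the conflict between the two scales, the mismatch between weekly and the calendar, the absence of a rule for unhealed grafts, and the missing unit and denominator in Section 12.7. The upper-bound effect at nominal days and the 14/15 against 20/21 comparison are plain arithmetic. That the summary would in practice cover healed grafts only is a likely reading of a silent plan, not something it states. The recorded means, SDs and coverage figures depend on assumed healing times, evenly spread windows, assumed extra visits and an assumed number of bilateral patients; they show direction and rough size only.

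**What to change.** - **Definition.** Reconcile the synopsis with Sections 10.1.2, 10.1.3 and 12.4.2 on one healing scale, and report the other as secondary.
- **Timing.** Delete weekly. Record actual days from surgery at every visit, extra ones included. Keep the first-visit mean as a labelled descriptive figure with the number of grafts it covers.
- **Main summary.** Add the proportion of patients whose engrafted grafts have all healed by one pre-named visit, with an exact binomial interval on that same patient-level proportion. Give per-graft proportions at the Day 14, 28, 42 and 90 visits descriptively.
- **Failures and losses.** In the analysis, count failed, removed or re-grafted grafts as not healed, and report second grafts separately. If follow-up is incomplete, show the proportion with lost patients counted as not healed and again with them excluded.
- **Section 12.7.** State the same unit, denominator and time point for the healing rate.
- **Section 10.3.** Handle time to 50% and 75% healing in the same way.

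The cost is protocol and analysis wording, with no new visits, patients or readers. Exact intervals will be wide (15/15: 78 to 100%; 14/15: 68 to 99.8%), and the healing figure may look less favourable once failures are counted.
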